### 9.1.2 Handling Missing Data.

The linear mixed-effects framework is an intent-to-treat framework in the sense that it uses all available data at all time-points. So if there are missing outcome values in any phase due to patient dropout, the usual analysis will still be valid. If the proportion of dropouts is substantial (20% or more) in either arm, then we shall also perform a weighted analysis with weights equal to the inverse of the probability of dropout. On the other hand, missing covariate values for the subject-level information will be imputed using multiple imputation methods. All missing values will be imputed using the chained equation method. The advantage of using this technique is its flexibility in allowing different types of variables (categorical and continuous) to be imputed together without requiring any multivariate joint distributional assumption. In this method, the missing values are sequentially updated using bootstrap or Markov Chain Monte Carlo based on multiple regression models with other variables as covariates. This procedure will be carried out for a number of repetitions or cycles, thereby constructing an 'imputed' dataset. Ten such 'imputed' datasets will be used for the final analysis, a number which is considered adequate for most applications. Finally we shall combine the results from the ten regressions with the imputed data using Rubin's formula. The multiple imputation method uses the assumption that the missing-ness conforms to a *missing at random* pattern which allows missing-ness in a variable X to depend on other covariates but does not allow it to depend on X itself. All analyses will be carried out in the statistical software SAS version 9.2.

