### **3.0 PRELIMINARY DATA**

#### 3.1 Study 1: Self-administered for Fatigue in Breast Cancer Survivors 

A total of 424 survivors of stages 0 to III breast cancer who had completed cancer treatments at least 12 months previously were screened, and 288 were randomized, with 270 receiving relaxing acupressure (n = 94), stimulating acupressure (n = 90), or usual care (n = 86). One woman withdrew owing to bruising at the acupoints. At week 6 (post-treatment), the percentages of participants who achieved normal fatigue levels (Brief Fatigue Inventory score <4) were 66.2% (49 of 74) in relaxing acupressure, 60.9% (42 of 70) in stimulating acupressure, and 31.3% (26 of 84) in usual care. At week 10, a total of 56.3% (40 of 71) in relaxing acupressure, 60.9% (42 of 69) in stimulating acupressure, and 30.1% (25 of 83) in usual care continued to have normal fatigue (see Figure 1). At neither time point were the 2 acupressure groups significantly different. Relaxing acupressure, but not stimulating acupressure, showed significant improvements in sleep quality compared with usual care at week 6, but not at week

Figure 1. Effect of Two Types of Acupressure on Fatigue (Grey area represents normal fatigue levels <4 on BFI) 10. Only relaxing acupressure significantly improved quality of life vs usual care at weeks 6 and 10.

Both acupressure arms significantly reduced persistent

fatigue compared with usual care, but only relaxing acupressure had significant effects on sleep quality and quality of life. Relaxing acupressure offers a possible low-cost option for managing symptoms.

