### 4.4 Blinding.

The three acupressure formulas (relaxing, stimulating and sham) will be labeled acupressure set "A", set "B", and set "C". Acupressure educators, outcome assessors, study participants, and study investigators (who will not interact with any of the study participants) will be blinded as to acupressure allocation. Only after data analysis is completed will the randomization code be unblinded. Those randomized to usual care will know that they are not receiving acupressure.

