### 7.2.3 New illness or Medication

Participants, who are diagnosed with a new chronic illness, start a new prescribed chronic medication (taking medication continuously for longer than 10 days) or have an increase in medication dose during the study period, will be withdrawn from the study and replaced by another participant. Participants who experience an acute illness (less than 2 weeks) e.g., a cold or receive acute medications will have these documented but will remain in the study.

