### 9.2 Sample Size Justification

Power is computed via simulation using LMM with a group, week, group by week interaction, and a random subject effect. Mean BFI values at week 6 are taken to be 4, 3, 2 at the end-treatment point for usual care, stimulating acupressure, and relaxing acupressure. The between-subject variance is assumed to be 4 at all time-points; whereas the variance of the random subject component was also 4 with an intra-class correlation of 0.5. For this configuration, power for detecting group differences is > 0.80 and power for detecting a significant week by group interaction is 0.62 with a sample size of 15 per treatment arm and 5% level of

significance. We assume a 16 to 17% drop-out rate based on previous studies and thus plan to recruit 18 per arm to ensure that 15 participants complete the entire 10-weeks of the study.

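### The drop-out sensitivity analysis in section 9.1.2 inverts its weights: it uses 1/P(dropout) where 1/P(remaining observed) is needed

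*Combined protocol and SAP*

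**What the plan says.** Section 9.1.2 relies on a linear mixed model fitted to all available data as the main protection against drop-out, and adds a conditional check. The condition is "If the proportion of dropouts is substantial (20% or more) in either arm". The check is "we shall also perform a weighted analysis with weights equal to the inverse of the probability of dropout". Read plainly, the weight is w = 1/P(dropout).

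No other section redefines the weight. The plan gives no drop-out model, no covariates for one, and no account of how the weights enter the mixed model.

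On expected drop-out, section 9.2 says: "We assume a 16 to 17% drop-out rate based on previous studies and thus plan to recruit 18 per arm".

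**The concern.** Weighting for drop-out lets the participants who stay stand in for similar participants who left. Someone with a 70% chance of staying represents 1/0.70 people like herself. Weighting by 1/P(dropout) does the reverse: it favours those who were never likely to leave, and the weight has no upper bound as drop-out risk approaches zero.

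The check exists to show whether the main result survives substantial drop-out. Applied literally as participant weights, it biases an arm mean whenever drop-out risk varies with predictors of BFI, and it biases the between-arm contrast when that dependence differs by arm. The check could then contradict a valid main analysis, or falsely reinforce it.

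Dependence that differs by arm is plausible here. Section 4.4 notes of the control arm: "Those randomized to usual care will know that they are not receiving acupressure". In Study 1 (section 3.1) the week-6 denominators also fell unequally across arms. That shows different rates, not who left, and a difference in rates is not enough by itself to bias the contrast.

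**Working it through.** **The plan's own drop-out figure.** Section 9.2 needs 15 completers per arm. 15/(1−0.16) = 17.86, 15/(1−1/6) = 18.00 and 15/(1−0.17) = 18.07, so 18 per arm is reproduced. The weight rule has no stated numerical result to reproduce.

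**Individual weights (illustrative risks).**

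| Drop-out risk | As written, 1/p | Correct, 1/(1−p) |
|---|---|---|
| 10% | 10 | 1.11 |
| 38% | 2.6 | 1.61 |

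**Two-stratum example (assumed values).** Equal strata have mean BFI 3 and 5, so the full-cohort mean is 4.00. Drop-out is 10% and 30%, so completers make up 0.45 and 0.35 of the cohort.
- Unweighted: (0.45×3 + 0.35×5)/0.80 = 3.875.
- As written, weights 10 and 3.33: (4.5×3 + 1.167×5)/5.667 = 3.41.
- Correct, weights 1/0.9 and 1/0.7: (0.5×3 + 0.5×5)/1 = 4.00.

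Here the written rule is worse than no weighting. With 20% drop-out in both strata, all three give 4.00.

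**Effect on the treatment contrast.** Inputs from section 9.2: week-6 mean BFI of 2 (relaxing) and 4 (usual care), so the true contrast is −2; random-subject variance 4 and intra-class correlation 0.5, hence residual variance 4. Assumed: mean BFI at weeks 0/2/6/10 of 6/4/2/2 (acupressure) and 6/5/4/4 (usual care); drop-out after week 2 in the acupressure arm with logit(p) = a + b×(week-2 BFI − arm mean), and a set to give 22.2% (4 of 18).

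Among completers the written rule gives net weight (1−p)/p = exp(−(a + bx)), where x is the centred week-2 BFI. For normal scores this shifts the week-6 arm mean by −b×Cov(week 2, week 6) = −4b, whatever the drop-out rate. Simulation with 1,000,000 per arm gave these week-6 contrasts:

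| Slope b per BFI point | Unweighted LMM | Correct weights | As written, completers | As written, all participants weighted |
|---|---|---|---|---|
| 0.1 | −2.00 | −2.00 | −2.40 | −2.31 |
| 0.2 | −2.00 | −2.00 | −2.80 | −2.65 |
| 0.3 | −2.00 | −2.00 | −3.19 | −3.02 |

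The closed form gives −2.40, −2.80 and −3.20. At b = 0.2, drop-out risk runs from 11% to 35% between the 10th and 90th percentiles.

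Other cases:
- b = −0.2 (less fatigued participants leave): −1.20.
- b = 0.2 in both arms: −2.00, although both arm means are 0.80 too low.
- b = 0.2 in both arms, with drop-out 22.2% against 2.3%: −2.00 (completers) or −1.87 (all weighted).
- Constant risk: −2.00.
- Weights used only as residual-precision weights in a correctly specified mixed model with known variances, run at b = 0.3: −2.00.

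**How likely the check is to be run.** With 18 per arm, 3 drop-outs (16.7%) do not meet the 20% trigger and 4 (22.2%) do. Let q = P(Bin(18, p) ≥ 4); the chance for at least one of four arms is 1−(1−q)^4.

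| p | q | At least one of four arms |
|---|---|---|
| 0.16 | 0.323 | 0.79 |
| 1/6 | 0.352 | 0.82 |
| 0.17 | 0.367 | 0.84 |

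This ignores the replacement of withdrawn participants in sections 7.2.3 and 7.2.4.

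**Study 1, week 6.** The numbers treated were "with 270 receiving relaxing acupressure (n = 94), stimulating acupressure (n = 90), or usual care (n = 86" and the week-6 results "were 66.2% (49 of 74) in relaxing acupressure, 60.9% (42 of 70) in stimulating acupressure, and 31.3% (26 of 84) in usual care". The shortfalls are 1−74/94 = 21.3%, 1−70/90 = 22.2% and 1−84/86 = 2.3%.

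**The case against.** The wording error itself is not in dispute; the case on the other side is about its weight.

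- **Shorthand.** The sentence may be loose wording for standard inverse-probability weighting, and a competent analyst would probably notice. That is possible, but nothing in the documents says so. A pre-specified analysis should be executable as written, and silently using the correct weight would be an undocumented departure.
- **Limited reach.** The analysis is supplementary and conditional, in a pilot whose aims are feasibility and exploration. This stands: no primary conclusion rests on the phrase.
- **Assumed size.** The slopes, their restriction to one arm and the remaining BFI means are not in the documents. This stands, so the contrasts are an illustration and not an expected bias.
- **Variance reading.** Section 9.2 calls the between-subject variance 4 and continues: "whereas the variance of the random subject component was also 4 with an intra-class correlation of 0.5". If total variance is 4, the covariance is 2 and the shifts halve to −0.2, −0.4 and −0.6. Clipping scores to the 0–10 range of the BFI reduces them to −0.27, −0.50 and −0.70 (total variance 8) or −0.16, −0.32 and −0.46 (total variance 4). The clipped shifts are below one standard error of a two-arm week-6 contrast with 15 per arm: √(2×8/15) = 1.03 or √(2×4/15) = 0.73. The size is sensitive to these choices; the existence of the bias is not.
- **Trigger probability.** It assumes equal, independent drop-out in all arms and ignores participants who "will be withdrawn from the study and replaced by another participant". Leaving usual care out altogether gives 1−(1−q)^3 = 0.69, 0.73 and 0.75, so the trigger remains within reach.
- **Study 1.** The section gives no reason for the smaller week-6 denominators, so calling them losses is an inference. This is fair.

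**Conclusion.** The concern holds. As written, the rule defines the wrong weight, and no other section corrects it. Where drop-out risk depends on predictors of BFI, participant weights of 1/P(dropout) move an arm mean away from the full-cohort value. Under the normal random-intercept illustration the completer shift is −4b, or −2b if total variance is 4. The contrast is biased only if the dependence differs by arm, and its direction depends on who leaves. There is no bias with constant risk, and none was seen when the weights acted only as residual-precision weights.

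This should be fixed, but it does not undermine the trial: the main mixed model, the sample size and the power statement do not use these weights.

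**What to change.** In section 9.1.2, define the weights as the inverse of the estimated probability of remaining in the study (1 minus the probability of dropout) at each visit. As a wording correction for a four-arm trial, make the 20% trigger refer to 'any' arm instead of 'either' arm. The cost is one phrase and one word, with no effect on data collection, participants or sample size.

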### 9.2 Sample Size Justification

Power is computed via simulation using LMM with a group, week, group by week interaction, and a random subject effect. Mean BFI values at week 6 are taken to be 4, 3, 2 at the end-treatment point for usual care, stimulating acupressure, and relaxing acupressure. The between-subject variance is assumed to be 4 at all time-points; whereas the variance of the random subject component was also 4 with an intra-class correlation of 0.5. For this configuration, power for detecting group differences is > 0.80 and power for detecting a significant week by group interaction is 0.62 with a sample size of 15 per treatment arm and 5% level of

significance. We assume a 16 to 17% drop-out rate based on previous studies and thus plan to recruit 18 per arm to ensure that 15 participants complete the entire 10-weeks of the study.

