# 2.0 SPECIFIC AIMS

- 1. To determine the feasibility of recruiting and conducting acupressure in fatigued persons with lupus
- To explore the effect of two distinct acupressure formulas (relaxing and stimulating) plus usual care versus sham acupressure plus usual care and usual care alone on severity and impact of chronic fatigue (as measured by the Brief Fatigue Inventory)
  - a. Hypothesis: Both relaxing and stimulating acupressure are superior to sham acupressure and usual care, but relaxing acupressure is superior to stimulating acupressure

- 3. Secondary: To explore the effect of two distinct acupressure formulas (relaxing and stimulating) plus usual care versus sham acupressure plus usual care and to usual care alone on quality of life, sleep and pain
  - a. Hypothesis: Both relaxing and stimulating acupressure are superior to sham acupressure and usual care, but relaxing acupressure is superior to stimulating acupressure

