# 4.3 Randomization and Stratification.

Our randomization scheme will be created by our study statistician. Eligible patients will be randomized into one of four groups: once daily relaxing acupressure, once daily stimulating acupressure, once daily sham acupressure or usual care in a 1:1:1:1 ratio for a total of 72 participants with 18 randomized into each group.

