## 9.1 Primary and Secondary Aims

To investigate the change through time both within and between groups for fatigue (BFI), we will use linear mixed models (LMM). An advantage of LMM is that it acts as essentially an intent-to-treat (ITT) analysis as it uses all available data at each time point. For each LMM, a random subject intercept will be included to account for subject clustering; visit, group, and the interaction term (visit by group), will also be included as fixed effects. The models for BFI will be controlled for the fixed effects of any baseline variable such as age or lupus disease activity that is significantly different at baseline. Normality of the residuals derived from the LMM will be assessed using the Shapiro–Wilk test and q-q plots. For non-normal results a Box-Cox transformation will be utilized. The same methods will be employed to investigate secondary outcomes of interest pain (BPI severity sub-scale), sleep (PSQI global score) and quality of life (RAND SF-36).

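### Section 9.2 states power above 0.80 for group differences, but this cannot be reproduced from its inputs and is out of reach for the omnibus group term of the model it names

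*Combined protocol and SAP*

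**What the plan says.** Section 9.2 describes the method as follows: "Power is computed via simulation using LMM with a group, week, group by week interaction, and a random subject effect". The model as described has no baseline covariate. Week-6 means of 4, 3 and 2 are given "at the end-treatment point for usual care, stimulating acupressure, and relaxing acupressure". No mean is given for sham, and none for any arm at baseline, week 2 or week 10, although sections 4.6 and 4.7 collect the BFI at all of these.

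On variability, the section says "The between-subject variance is assumed to be 4 at all time-points" and continues: "whereas the variance of the random subject component was also 4 with an intra-class correlation of 0.5".

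The result is stated as "For this configuration, power for detecting group differences is > 0.80", together with 0.62 for the week-by-group interaction, both for 15 per arm at the 5% level. The test behind the first figure is not named.

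The design has four arms (section 4.3): "in a 1:1:1:1 ratio for a total of 72 participants with 18 randomized into each group". The Aim 2 hypothesis in section 2.0 reads: "Both relaxing and stimulating acupressure are superior to sham acupressure and usual care, but relaxing acupressure is superior to stimulating acupressure". That makes five pairwise contrasts, two of them against sham.

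**The concern.** Power above 0.80 looks too high for 15 per arm when the standard deviation at a single visit is √8 ≈ 2.8 points and neighbouring arms differ by 1 point. The two variance statements also sit badly together. If the first means the total variance at a visit, it contradicts the second.

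A reader of section 9.2 would conclude that the trial has a better than 80% chance of detecting the assumed differences between arms. A non-significant comparison between the two formulas, or against sham, could then be taken as evidence of no effect when a later trial is planned. At the stated variances such a result would say little.

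**Working it through.** **Inputs from section 9.2:** n = 15 per arm; means 4, 3, 2; random-subject variance σ_b² = 4; ICC = 0.5. Section 9.0 gives two-sided tests at 0.05.

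**Assumed, because not stated:** a sham mean between 2 and 4; a common baseline, as expected under randomisation; and effects at other visits no larger than at week 6, unless noted.

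**Residual variance.** ICC = σ_b²/(σ_b² + σ_e²), so 0.5 = 4/(4 + σ_e²). This gives σ_e² = 4 and a total of 8.

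**Group term.** In a balanced random-intercept model with T visits and G arms, λ = n·Σ(arm mean − overall mean)²/(σ_b² + σ_e²/T), where arm means are averaged over visits. Power comes from the noncentral F with G − 1 and G(n − 1) degrees of freedom.

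**Step 1: an upper limit.** Let the residual contribution σ_e²/T fall to zero and suppose the full week-6 differences hold on average over all visits.

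| Arms | Sum of squares | λ = 15 × SS/4 | Power |
|---|---|---|---|
| Three | 2.00 | 7.50 | 0.65 |
| Four, sham 3 | 2.00 | 7.50 | 0.59 |
| Four, sham 2.5 or 3.5 | 2.1875 | 8.20 | 0.63 |
| Four, sham 2 or 4 | 2.75 | 10.31 | 0.74 |

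**Step 2: a common baseline.** The most favourable case has visits at weeks 0, 2, 6 and 10 with the full effect from week 2. Visit-averaged differences are then 3/4 of those at week 6, so SS is multiplied by 0.5625. The denominator is 4 + 4/4 = 5.

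- Three arms: λ = 15 × 2 × 0.5625/5 = 3.375, power 0.34.
- Four arms, sham 3: λ = 3.375, power 0.29.
- Four arms, sham 4: λ = 15 × 2.75 × 0.5625/5 = 4.64, power 0.39.

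**Step 3: the largest single contrast.** For relaxing versus usual care at week 6 (2 points), the standard error is √(2 × 8/15) = 1.03. Noncentral t with 28 df gives power 0.46 without baseline adjustment. A 1-point contrast has about 0.15.

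**Step 4: total variance 4 (2 + 2).** The step 2 denominator becomes 2 + 2/4 = 2.5.

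- Three arms: λ = 16.875/2.5 = 6.75, power 0.61.
- Four arms, sham 3: λ = 6.75, power 0.54.
- Four arms, sham 4: λ = 23.203/2.5 = 9.28, power 0.69.

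The group term therefore stays below 0.80 on this reading too. Some other tests do pass at 2 + 2:

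- Group term on post-baseline visits only, full effect from week 2: λ = 30/(2 + 2/3) = 11.25, power 0.83 (three arms); 0.78 (sham 3); about 0.90 (sham 4).
- Joint test of group and interaction, categorical visit: up to about 0.85, 0.79 and 0.92 in the same order.
- Relaxing versus usual care at week 6, baseline-adjusted: 0.86.

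**The interaction figure.** At 4 + 4, the largest interaction power is 0.48 (three arms) or 0.55 (sham 4) with categorical visit, and 0.59 or 0.68 with linear week. So 0.62 can be neither confirmed nor excluded.

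**The case against.** The strongest reply is that section 9.2 never says which test its figure refers to, so a limit on the omnibus group term does not refute it. This stands. At 4 + 4 there are routes past 0.80:

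- **Baseline covariate with averaging over weeks 2, 6 and 10.** If the full effect is present from week 2, the variance is (4 + 4/3) − 4²/8 = 3.33, and relaxing versus usual care has power 0.82. The model in section 9.2 has no such covariate. Section 9.1 adjusts only for "any baseline variable such as age or lupus disease activity that is significantly different at baseline".
- **Effects that keep growing to week 10.** With linear divergence, the joint test with linear week reaches 0.89 (three arms), 0.85 (sham 3) or 0.95 (sham 4). The group term still stays at or below about 0.55. Acupressure stops at week 6 (section 4.7.4) and section 4.0 uses week 10 to look at persistence, so growth is not the natural assumption and is not stated.
- **Counting success as any one significant contrast.** A simulation with sham at 4 and full effect from week 2, averaging the post-baseline visits, gives 0.83. This inflates the type I error, and section 9.2 does not state it.

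A slip in the variance wording is also possible. At 2 + 2, with sham at 3 and the same effect at weeks 2, 6 and 10, the interaction has 0.60 to 0.63 and the joint test 0.80 to 0.82, close to both printed figures. That reading contradicts the sentence giving the random-subject component as 4.

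Finally, the trial is a pilot (section 1.2), feasibility is Aim 1, the efficacy aims are exploratory, and section 9.2 openly reports 0.62. This limits the consequence but does not supply the missing support for the power figure.

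**Conclusion.** The point holds in this form: the stated power is not reproducible from the section's inputs, and it is unattainable for the omnibus group term of the named model. At 4 + 4 the limit is 0.65 (three arms) or 0.59 to 0.74 (four arms), which rests on visit-averaged arm means being no further apart than 4/3/2 and, for four arms, on sham lying between 2 and 4. The 0.34 and 0.39 also need a common baseline and effects that never exceed those at week 6.

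Three stronger readings are not supported:

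- A reader might infer that no analysis could reach 0.80. Several can, under conditions the section does not state.
- A reader might infer that 0.62 is wrong as well. It cannot be verified as written, and no error is claimed.
- A reader might infer that 72 participants is the wrong number. For a pilot whose first aim is feasibility, the documents do not show that. What lacks support is the power statement, and the harm is confined to how null comparisons are read.

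**What to change.** Keep 72 participants and revise section 9.2 to state:

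- one consistent pair of subject and residual variances;
- the assumed means for all four arms, including sham, at each visit in the simulated model;
- whether week is categorical or linear;
- the exact test that group differences refers to.

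Then rerun the simulation and replace the figure above 0.80 with the result, reporting the interaction power from the same run.

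Optionally, add the expected 95% confidence interval half-width for a week-6 difference between two arms with 15 each, unadjusted: 2.048 × √(2 × 8/15) ≈ ±2.1 points at total variance 8, or 2.048 × √(2 × 4/15) ≈ ±1.5 at total variance 4. This is a suggestion only, since section 9.1 does not name a week-6 contrast.

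The cost is one rerun and a rewritten paragraph, with no extra participants and no change in procedures. The downside is that the stated power is likely to be less favourable.
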